### **7.4.3. Visit 04, Day 57, Clinic Visit (Window: 56±3 days post first study vaccination)**

- Interim medical history, including an assessment for new medical conditions will be obtained by interview of parent(s)/legal guardian(s) and any changes since the previous clinic visit or contact will be noted.
- Subject or subject's parent(s)/legal guardian(s) will be asked if the subject had any additional blood taken for medical reasons.
- AEs limited to AESIs, NOCMCs, and SAEs will be recorded on the appropriate data collection form.
- A targeted physical examination may be performed, if indicated based on review of interim medical history, by a study clinician licensed to make medical diagnoses and listed on the Form FDA 1572 as the site principal investigator or sub-investigator.
- Subject's/parent(s)/legal guardian(s) will be counseled on the avoidance of taking any aspirin or salicylate containing products for 30 days prior to receipt of the first vaccination through 21 days after the last vaccination.
- In the event that the subject attends the visit without a parent/legal guardian, the parent/legal guardian will be called to collect updated medical history, concomitant medications, and will be reminded that the subject is to avoid any aspirin or salicylate containing products for 30 days prior to receipt of the first vaccination through 21 days after the last vaccination.
- A nasal swab for sIgA will be obtained.
- Approximately 6 mL of venous blood will be collected for serum HAI, HA/NA ELISA and neutralization assays.
- Approximately 16 mL of PBMCs will be collected for IFN- $\gamma$  ELISPOT and CFSE dilution/ICS assays.
- Approximately 4 mL of venous blood will be collected if Hgb level at Day 22 has dropped 0.5 g/dL or more from baseline or is < lower limit of normal. If results at Day 57 still meet that criteria ( $\geq 0.5$  g/dL drop from baseline or < lower limit of normal), no further PBMC collection will be done. If results have recovered to within 0.4 g/dL of baseline at Day 57, resume blood collection plan for the rest of the study.

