#### **7.4.4. Visit 05, Day 92, Second Vaccination (Dose 2), Clinic Visit (Window: 91±14 days post first study vaccination)**

- Interim medical history, including an assessment for new medical conditions will be obtained by interview of parent(s)/legal guardian(s) and any changes since the previous clinic visit or contact will be noted.
- Criteria for administering QIV will be reviewed with parent(s)/legal guardian(s).
- Concomitant medications (limited to aspirin or salicylate containing products) will be recorded on the appropriate data collection form.
- All AESIs/NOCMCs/SAEs will be recorded on the appropriate data collection form. Reporting of AEs occurring since previous visit but before 2nd vaccination is limited to AESIs, NOCMCs, and SAEs.
- A targeted physical examination may be performed prior to the second study vaccination, if indicated based on review of interim medical history, by a study clinician licensed to make medical diagnoses and listed on the Form FDA 1572 as the site principal investigator or sub-investigator.
- Subject's/parent(s)/legal guardian(s) will be counseled on the avoidance of taking any aspirin or salicylate containing products for 30 days prior to receipt of the first vaccination through 21 days after the last vaccination.
- Oral temperature will be obtained to ensure eligibility. Subjects must not eat or drink anything hot or cold, or smoke within 10 minutes prior to taking oral temperature.
- A urine pregnancy test will be performed on all female adolescent subjects of childbearing potential and must be negative to ensure eligibility.
- A nasal swab for sIgA will be obtained.
- Approximately 6 mL of venous blood will be collected for serum HAI, HA/NA ELISA and neutralization assays.
- Approximately 16 mL of PBMCs will be collected for IFN- $\gamma$  ELISPOT and CFSE dilution/ICS assays. Note: PBMCs will not be collected if the HgB was consistently low through Day 57.
- Subjects will receive their second vaccination IM in whichever deltoid they prefer.

- Subjects will receive a single dose of study vaccine via IM injection into the deltoid muscle of the preferred arm. The site of injection and time of administration will be recorded on the appropriated data collection form. Subjects will be observed in the clinic for at least 30 minutes after the second study vaccination.

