PBMC (IFN- $\gamma$ ELISPOT and CFSE Dilution/ICS Assays)		X	X	X	X	X 	X 			X 	
Enrollment in AdvantageEDC SM and Randomization		X									
Pre-Administration Reactogenicity		X				X					

Study Visit Number	V00	V01	V02	V03	V04	V05	V06	V07	V08	Early Term	Unscheduled
Study Day post first study vaccination	Screen -28 to -1	Dose 1* D1	D8 ±1	D22 ±2	D57 ±3	Dose 2* D92 ±14	D 113	D 240	D 366		
Study Day post second study vaccination						D1	D22 ±2	D149 ±14	D275 ±14		
Study Vaccination		X				X					
30-minute Evaluation After Study Vaccination		X				X					
Distribute Memory Aid and Study-Related Materials		X									
Review Memory Aid			X							X@	X@
AE Assessment		X	X	X						X#	X#
AESI + NOCMC Assessment			X	X	X	X				X'	X'
SAE Assessment		X	X	X	X	X	X	X	X	X	X
Phone Call								X	X		

- { } Targeted physical examination if indicated based on review of complete or interim medical history
- ^ Will be performed on all female adolescents of childbearing potential at screening and within 24 hours prior to each study vaccination and results must be negative and known prior to each study vaccination.
- # If within 21 days post first study vaccination.
- \* On dose dates, samples must be collected pre-dose
- @ If within 8 days after 1st vaccination
-  If within 3 months post first study vaccination
-  Subject's parent(s)/legal guardian(s) will be asked if the subject had any additional blood taken for medical reasons.  
subject's blood taken for medical reasons
-  Concomitant medications will be limited to collecting aspirin and salicylate containing products
-  Aspirin or salicylate containing products will be collected if within 30 days of the first vaccination through 21 days after the last vaccination
-  Hemoglobin only
-  Collect at Day 22 if Hgb results from screen to Day 8 drop  $\geq 0.5$  g/dL or < lower limits of normal
-  If Hgb is not collected at Day 22 or low at Day 22, collect at Day 57
-  Will not collect PBMCs if Day 57 HgB is low

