3.2.2. Secondary

Immunogenicity:

- For HAI and Neutralizing antibody responses, percentage of subjects achieving seroconversion (defined as either a pre-vaccination titer $<1:10$ and a post-vaccination titer $\geq 1:40$, or a pre-vaccination titer $\geq 1:10$ and a minimum four-fold rise in post-vaccination antibody titer) against H3N2 M2SR-like and H3N2 QIV-like viruses at approximately 7, 21, and 56 days following receipt of the first study vaccination and immediately prior to and approximately 21 days following receipt of QIV.
- For HAI and Neutralizing antibody responses, percentage of subjects achieving a serum antibody titer of 1:40 or greater against the H3N2 M2SR-like virus and the H3N2 QIV-like virus at baseline and approximately 7, 21, and 56 days following receipt of the first study vaccination and immediately prior to and approximately 21 days following receipt of QIV.
- For HAI and Neutralizing antibody responses, the geometric mean titers (GMTs) and geometric mean fold rise (GMFR) to H3N2 M2SR-like virus and H3N2 QIV-like virus at baseline and approximately 7, 21, and 56 days following receipt of the first study vaccination and immediately prior to and approximately 21 days following receipt of QIV.
- GMT and GMFR of nasal sIgA responses directed against the H3N2 M2SR virus and the H3N2 QIV virus measured by EPT(ELISA) with and without normalization to total sIgA at baseline and approximately 7, 21, and 56 days following receipt of the first study vaccination and immediately prior to and approximately 21 days following receipt of QIV.
- Frequency of influenza H3 HA-specific (H3 M2SR-like and QIV-like viruses) and conserved internal viral protein-specific IFN- γ ELISPOT responses at baseline and approximately 7, 21, and 56 days following receipt of the first study vaccination and immediately prior to and approximately 21 days following receipt of QIV.

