4.3. Selection of Study Population

The study population for this clinical trial is 50 male and non-pregnant female children and adolescents between the ages of 9 and 17 who are in good health and meet all eligibility criteria. Specific eligibility criteria can be found in the protocol sections 5.1 (Subject Inclusion Criteria) and 5.2 (Subject Exclusion Criteria). The subjects are recruited from the general population at the participating Vaccine Trial and Evaluation Unit (VTEU) site, Saint Louis University (SLU), which has substantial experience conducting influenza vaccine studies.

Following review of laboratory results for subjects enrolled through August 2018, it was identified that a significant portion had a drop in hemoglobin during the study. The protocol was amended to include screening for pre-existing iron deficiency anemia with ferritin and requiring both normal ferritin and HgB results for enrollment, to reduce the amount of blood collected overall, and to add a contingency regarding specimen collection. Subjects will be monitored after entry in the trial for drops in hemoglobin levels indicating anemia. If HgB levels are consistently low through the visit at approximately Day 57, the subject will no longer have PBMC samples collected at subsequent visits.

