6.5. Missing Data

All attempts will be made to collect all data per protocol. As missing data are expected to be minimal, no imputation will be performed for missing values [2]. Any data point that appears to be erroneous or inexplicable based on clinical judgment will be investigated as a possible outlier. If such data points are identified as scientifically valid outliers, sensitivity analyses will be performed to examine the impact of including or excluding the outliers. Any substantive differences in these analyses will be reported.

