9.6. Clinical Laboratory Evaluations

Clinical laboratory parameters to be evaluated at the Screening Visit (Visit 00) and on Day 08 (Visit 02) will include a White Blood Cell Count (WC), HGB, HCT (only at Visit 00), Platelet Count, ALT, AST, Serum Creatinine, Ferritin (at Visit 00), Prothrombin Time (PT) and Activated Partial Thromboplastin Time (aPTT). The grading scales for clinical laboratory evaluations are presented in Table 11 and Table 10. Clinical laboratory evaluations assessed on Day 1 prior to the first study vaccination will be considered as baseline.

Subjects with HGB below the lower limit of normal (LLN) at Day 8, or subjects who experience a drop of ≥ 0.5 g/dL between screening and Day 8, will have HGB re-drawn at Day 22. If HGB remains low (result is less than LLN or ≥ 0.5 g/dL lower than screening levels) at Day 22, or if HGB is not collected at Day 22, hemoglobin labs will be re-drawn at Day 57. Any subject where HGB results remain low at Day 57 will have no further PBMC collected. HGB and Ferritin will be drawn for all subjects at Day 113 (approximately 22 days post QIV vaccination). Ferritin results taken at Day 57 will be used for clinical decision making only – values will not be graded or included in summaries of clinical laboratory data, but will be included in the listings of hematology results (Listing 15).

The distribution of laboratory results by severity, study day and treatment group will be presented beginning with [Table 54](#), and continuing through [Table 65](#). Descriptive statistics including mean, standard deviation, median, minimum and maximum values and change from baseline by study day will be summarized for each parameter in [Table 59](#) and [Table 67](#). Box plots illustrating the change from baseline for each laboratory parameter will be presented in [Figure 56](#), [Figure 57](#), [Figure 58](#), [Figure 59](#), [Figure 60](#), [Figure 61](#), [Figure 62](#), and [Figure 63](#). Subject visits with abnormal laboratory results, Grade 1 severity or higher, will be presented in [Table 52](#) and [Table 53](#) for chemistry and hematology parameters, respectively. Abnormal results will be summarized by visit and study arm in [Table 58](#) and [Table 66](#) for chemistry and hematology parameters, respectively.

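### PBMC collection stops after Day 57 in children with persistently low HGB, so Day 92 and Day 113 ELISPOT data are missing by rule, but the SAP treats missing data as minimal and summarizes available cases only

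*SAP*

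**What the plan says.** SAP 3.2.2 lists among the secondary endpoints: "Frequency of influenza H3 HA-specific (H3 M2SR-like and QIV-like viruses) and conserved internal viral protein-specific" IFN-gamma ELISPOT responses. The time points are baseline, about 7, 21 and 56 days after the first vaccination, immediately before QIV and about 21 days after QIV. SAP 4.1 confirms that the assay runs on PBMC.

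The stop rule appears in both documents. SAP 4.3 states "If HgB levels are consistently low through the visit at approximately Day 57, the subject will no longer have PBMC samples collected at subsequent visits", and SAP 9.6 states "Any subject where HGB results remain low at Day 57 will have no further PBMC collected", with low meaning below the lower limit of normal or at least 0.5 g/dL under screening. Protocol 7.4.3 says that if Day 57 HGB still meets the criterion, "no further PBMC collection will be done". Protocol 7.4.4 (Day 92) notes that "PBMCs will not be collected if the HgB was consistently low through Day 57", and 7.4.5 (Day 113) repeats the note. Footnote 7 of protocol Appendix A reads: "Will not collect PBMCs if Day 57 HgB is low". SAP Table 2 marks PBMC at V05 and V06 without that footnote.

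SAP 4.3 gives the reason for the amendment: among children enrolled through August 2018, "a significant portion had a drop in hemoglobin during the study". The same section adds ferritin screening, requires normal ferritin and HGB at entry, and reduces the blood collected.

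On analysis, SAP 6.5 says: "As missing data are expected to be minimal, no imputation will be performed for missing values". Its sensitivity analyses concern outliers only. SAP 8 and Tables 34-37 give means, medians and fold rises for children with a result at each visit, and SAP 8 also plans differences between arms.

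**The concern.** A child whose HGB stays low has ELISPOT values through Day 57 and none afterwards, because the plan itself says so. The per-assay mITT definition in SAP 6.3.1 needs only a baseline and one post-vaccination result, so such a child counts in N throughout while leaving n at Days 92 and 113.

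The trigger is measured after randomization, and SAP section 12 reports consistent HGB falls after the first vaccination in 2018. The loss is therefore not completely at random, and balance between arms is not guaranteed. The Day 92 and Day 113 rows, and the late part of the frequency plots (SAP Figures 14-17), may describe a different set of children from the Day 1-57 rows. A shift in mean frequency between Day 57 and Day 92, or an arm difference at the late visits, can then mix immune response with a change in who was sampled. In a trial whose stated purpose is preliminary estimation, that affects the result itself.

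**Working it through.** **The plan's own allowance.** SAP section 5 allows 10% dropout: 25 x (1 - 0.10) = 22.5, rounded down to 22 per arm, which reproduces the stated figure. The allowance is 25 x 0.10 = 2.5 children per arm, so three HGB-driven stops in an arm would use it up before any ordinary dropout. It was set for the responder proportions in Table 4 and not for ELISPOT, so it is a yardstick only.

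**How many children might be stopped.** The documents give neither a rate of low HGB at Day 57 nor an HGB SD, so these inputs are assumptions. Per-draw within-child SD is taken as 0.3, 0.4 or 0.5 g/dL, with values rounded to 0.1 g/dL. Stopping requires screening minus current HGB to be at least 0.5 g/dL at Days 8, 22 and 57, all compared with the same screening draw. Simulating 400,000 children gives:

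| True fall at Days 8/22/57 (g/dL) | P(stopped) at SD 0.3 / 0.4 / 0.5 |
|---|---|
| 0 / 0 / 0 | 0.029 / 0.056 / 0.080 |
| 0.2 / 0.3 / 0.3 | 0.119 / 0.147 / 0.165 |
| 0.5 / 0.5 / 0.5 | 0.295 / 0.285 / 0.278 |

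The simulation ignores the below-normal trigger, which could only add cases. It also ignores the new screening and the lower blood volume, which may reduce them.

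**Base.** SAP section 12 has 31 children still to enroll in 2019. If the rule reached only them, the fraction missing among the 50 is m = P x 31/50.
- Lowest: 0.029 x 31 = 0.9 children, m = 0.018.
- Middle row: 0.119 to 0.165, m = 0.074 to 0.102.
- Highest: 0.295 x 31 = 9.1 children, m = 0.183.

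**Effect on one arm's late mean (n = 25), loss spread evenly.** The available-case SE is multiplied by 1/sqrt(1 - m). If stopped children differ by 0.5 SD in response (assumed), the mean shifts by 0.5m SD, which in SE units is 0.5m x sqrt(25(1 - m)).
- m = 0.018: SE x 1.009; shift 0.04 SE.
- m = 0.074 to 0.102: SE x 1.04 to 1.06; shift 0.18 to 0.24 SE.
- m = 0.183: SE x 1.106; shift 0.41 SE.

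**Effect on the arm difference.** With the same 0.5 SD gap in both arms, the shift is 0.5 x (m_A - m_B) SD. Equal loss gives zero. If 9 stops split 6 and 3, it is 0.5 x (6/25 - 3/25) = 0.06 SD, against an SE of sqrt(1/19 + 1/22) = 0.313 SD, or about 0.19 SE.

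**The case against.** The case for leaving the plan alone has real force on size and consequence.

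- **Timing of the evidence.** The HGB falls that prompted the rule came before the ferritin and HGB screening and the reduced blood volume. Those steps may make stops uncommon. This stands as a reason not to assume a high rate; it does not justify calling the loss minimal without counting it.
- **The boost step.** Days 92 and 113 are lost together, so the rule does not alter who contributes to the pre-boost to post-boost change. Fold rise from baseline is also calculated within child. A reader might infer that the QIV boost effect is confounded with attrition; the documents do not support that. What remains exposed is the comparison of late rows with Day 1-57 rows, and the late arm means and differences.
- **Symmetry.** Scheduled blood volumes are the same in both arms. If phlebotomy drives the falls, losses should be similar and much of the bias in the difference cancels. That is plausible, but it needs the counts by arm to confirm it.
- **Existing reporting.** Tables 34-37 show n by visit and arm, Tables 61, 66 and 67 show HGB, and Listing 10 gives individual results. Table 13 has only a generic reason for an uncollected sample, and its mITT reasons refer to HAI. A reader could reconstruct the stops, but no table reports them.
- **Conditional assay.** SAP 4.1 makes ELISPOT contingent and defers its analysis to an addendum, while SAP 8 plans summaries now. The point applies whenever Tables 34-37 are produced.
- **Trigger wording.** Persistently low through Day 57 and low at Day 57 nearly coincide, because Day 57 HGB is drawn only if Day 22 was low or missed. They can diverge only when the Day 22 draw was missed.

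**Conclusion.** The point holds as a modest, correctable weakness in the analysis of one secondary endpoint at two visits. Missingness is built into the plan, is tied to a post-randomization measurement, and is not addressed in SAP 6.5 or SAP 8. HAI, neutralization and sIgA sampling are unaffected, and with no formal hypothesis the harm is to estimation and interpretation.

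The size is unknown. On the assumptions above it is roughly 2-18% of the 50 children, an available-case SE increase of about 1-11%, and a shift in a late arm mean of about 0.04-0.41 SE. The shift rests on a 0.5 SD response gap for which the documents offer no support. All of this assumes the rule reached only the 31 children planned for 2019; the documents do not say how far it applied to the 19 enrolled in 2018.

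A reader might infer that 20-30% of all 50 children would be missing, with SE up 12-20% and a shift of 0.45-0.63 SE. That applies to the whole trial a rate reached only in the most severe scenario and only among the 2019 children. Nor do the documents show that the arms lose different numbers of children, so bias in the arm difference is possible but not established.

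**What to change.** Leave the clinical rule to the sponsor and change the analysis text.

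1. In SAP 6.5, exempt ELISPOT from the expectation of minimal missing data and state that PBMC is missing by rule in some children.
2. In Table 13, give HGB-driven PBMC stops their own reason and count them by arm.
3. In Tables 34-37, add Day 1-57 summaries restricted to children with PBMC at Days 92 and 113, so that the time course can be read in a constant set of children.
4. Add one sensitivity analysis: a likelihood-based repeated-measures model of transformed ELISPOT over all visits, with arm, visit, arm by visit and baseline frequency. State that it is valid under missing-at-random. Do not condition the arm contrast on post-randomization HGB, since that can distort the contrast if M2SR affects HGB. Day 8-57 HGB may serve as an auxiliary variable, if used at all. Day 113 HGB should not, because it is drawn after PBMC has stopped.
5. Reconcile the trigger wording across protocol 7.4.4, 7.4.5 and Appendix A and SAP 4.3 and 9.6, and bring SAP Table 2 into line with the protocol schedule.

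No new samples are needed. The cost is SAP wording, some table rows, and a model in about 50 children. The model needs a transformation chosen in advance, because SAP 3.3 puts the assay's lower limit at 0. It extrapolates for stopped children from their earlier visits, so it supplements the raw summaries and does not replace them.

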4.4. Treatments

4.4.1. Treatments Administered

H3N2 M2SR or saline placebo is administered intranasally using the VaxINator device as the first study vaccination. All subjects receive licensed seasonal QIV via IM injection as the second study vaccination.

4.4.2. Identity of Investigational Product(s)

See the study protocol section 6.1 for details of study product formulation.

4.4.3. Method of Assigning Subjects to Treatment Groups (Randomization)

Enrollment/randomization will be performed through the enrollment module in the electronic data capture system, maintained by the SDCC.

Eligible subjects will be randomized and assigned in a 1:1 ratio to receive intranasal H3N2 M2SR or saline placebo, with stratification by site. The randomization is based on a variable blocked scheme to provide an approximately balanced allocation to the treatment groups during the study.

4.4.4. Selection of Doses in the Study

A first-in-human dose escalation trial in healthy adults has already been conducted with doses up to 1×10^8 TCID₅₀ of the experimental H3N2 M2SR vaccine without any safety issues. In addition, this highest dose resulted in the greatest immunogenicity for relevant serum antibody, mucosal antibody and T cell responses. Furthermore, the current study involves the oldest pediatric subjects (age 9-17 years old) and therefore the sponsor believed the maximum dose given in the first-in-human trial was appropriate for this study.

4.4.5. Selection and Timing of Dose for Each Subject

Each subject is randomly assigned to a study group which will define the product received for the first vaccination (H3N2 M2SR or placebo). The first vaccination takes place on the day of randomization. All subjects receive licensed QIV approximately 3 months after the first vaccination (protocol defined window of 77 to 105 days post first vaccination).

